7.1. Inclusion criteria

RC&Plasma cohort

- All trauma patients >1yr old requiring prehospital major haemorrhage protocol activation by pre-hospital team in London, or trauma team lead at the Royal London hospital.
- Haemorrhagic shock
- Patients who have started or have received at least one RC&Plasma unit in the prehospital setting because of haemorrhage

Comparator groups

RBC cohort (retrospective data)

All trauma patients who have been transfused RBC in the pre-hospital setting in London (and emergency department at RLH) from March 2015 to April 2018.

RBC and FFP cohort (prospective data)

All trauma patients who have started or have received at least one RBC and FFP unit in the pre-hospital setting because of haemorrhage at Newcastle and Oxford hospitals

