Objectives / aims	Secondary objectives Compare the impact of RC&Plasma transfusion with red blood cell (RBC) transfusion (retrospective data) and RBC and fresh frozen plasma (FFP) transfusion (prospective data from Newcastle and Oxford hospital) on: resuscitative effect (base excess, lactate), coagulation parameters, overall transfusion requirement, haemolysis, days in hospital and mortality, in trauma bleeding patients.			
Number of participants	140 in the RC&Plasma arm 200 in the RBC arm (retrospective) 150 in the RBC and FFP arm			
Inclusion and exclusion criteria	 Inclusion criteria All trauma patients requiring pre-hospital major haemorrhage protocol activation by the pre-hospital team because of haemorrhagic shock and for whom clinician has transfused a RC&Plasma component (in London), or RBC and FFP by either the Great North or Thames Valley Air Ambulance. Patients who have received at least one RBC unit in the pre-hospital setting because of trauma haemorrhage between March 2015 and April 2018 (retrospective cases) 			
Study duration	2 years			

5. Introduction

Uncontrolled bleeding due to trauma is associated with significant morbidity and mortality, and substantial costs to NHS. Early administration of fresh-frozen-plasma (FFP) and platelets in a high (near 1:1:1) ratio with red blood cells (RBC) reduces mortality, and this has now become standard of care for trauma patients who are bleeding. However, the logistics of delivering FFP together with RBC in the pre-hospital setting could delay transfer to hospitals (which could be detrimental), and also place additional demands on the clinical team. Availability of a component that contains red cells and plasma (RC&Plasma) in a single bag could overcome these challenges. Such component is available in the UK: however, it is not used routinely. Furthermore, the efficacy and safety relative to other transfusion strategies have not been investigated in randomised controlled trials.

The Royal London Hospital Major Trauma Service and the Helicopter Emergency Medical Service, have made a clinical decision to change standard treatment for the management of trauma patients who are bleeding in the pre-hospital setting, from the transfusion of RBC to the transfusion of RC&Plasma for 24 months.

The overall objectives of this project are to:

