7.2. Exclusion criteria

None

8. Study design

Feasibility, observational cohort study.

RC&Plasma transfusion will replace RBC transfusion in the pre-hospital setting in London, and will be available for transfusion in hospital at RLH for trauma patients >1yrs old. Operational and clinical data relating to administration of RC&Plasma component will be compared with historical data of RBC transfusion in the pre-hospital setting in London from March 2015 to April 2018.

Newcastle and Oxford hospitals will continue to administer RBC and FFP transfusion in the pre-hospital setting.

9. Study procedures

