9.2. Data collection

Operational data

Operational data regarding the deliverability and supply of blood will be collected on monthly basis from NHSBT and transfusion laboratory.

Clinical data (prospective)

Data will be collected from the clinical team at six sites. Once a case has been identified, the clinical team on each site will be asked to complete the CRF for case using a unique identification number – this will be a sequential number for each site. The completed CRF will be emailed to the central team at Barts Health Trust using nhs.net email accounts.

Study cases will not be contacted or approached for consent and NO identifiers (i.e. names, addresses, dates of birth, hospital or NHS numbers, or date of death) will be sought in the CRF. Respondents will be asked to keep their own record of the unique study number and the patient identifiers in order to facilitate elimination of duplicate reports or raise further gueries if required.

The CRF will be made up of two parts and will seek information as described in Table 1.

Table 1.	Variables that will be collected on the Case Report Form	
Part 1: At	presentation and within 24 hrs of blood transfusion in pre-hospital	
setting (or emergency department for RLH)		
- Gen	der and age	

- Co-morbidities

- Date of transfusion for RC&Plasma (and RBC and FFP)
- Number of units transfused (or ml/Kg for children)
- Donation number for each RC&Plasma transfused
- Amount of crystalloid/colloid administered in 24 hours
- Severity of injury
- Laboratory results (Haemoglobin, platelet, coagulation tests, lactate results) from scene to ED and within 24 hours
- Patient's blood group
- Blood transfusion requirements in the first 24 hours
- Time of death (in hours) from administration of RC&Plasma (or RBC only, or RBC and FFP), and cause of death
- Transfusion reactions

Part 2: At 30 days, or discharge, or death or transfer to another hospital, (whichever is first)

- Date of discharge
- Thrombotic event (arterial or venous)
- Blood transfusion requirements
- Transfusion reactions
- Number of ventilator free days
- Number of intensive care units-free days
- Hospital length of stay
- Time of death (in days) from administration of RC&Plasma (or RBC and FFP), and cause of death

Retrospective data

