Similar information as described in Table 1 will also be collected for trauma patients who have received RBC transfusion in the pre-hospital setting in London between March 2015 to April 2018. Cases will be initially identified from transfusion laboratories at RLH, and once the case has been identified other sites will be asked to submit anonymised clinical information on identified cases using patient's clinical notes and patient's electronic data.

Each case will be given a unique identifier, and no patient's identifier will be collected on the CRF or transferred to the central team at Barts Health.

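### Section 7.1 sets unequal entry rules for the three cohorts, and its emergency-department wording for the RBC comparator contradicts the rest of the protocol, so the secondary clinical comparisons are open to selection bias

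*Protocol*

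**What the plan says.** Section 7.1 of the protocol gives each cohort its own entry rule.

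- **RC&Plasma.** Patients are over 1 year old, "requiring prehospital major haemorrhage protocol activation by pre-hospital team in London, or trauma team lead at the Royal London hospital", in haemorrhagic shock, and must be "Patients who have started or have received at least one RC&Plasma unit in the prehospital setting because of haemorrhage".
- **RBC (retrospective).** "All trauma patients who have been transfused RBC in the pre-hospital setting in London (and emergency department at RLH", over the stated dates. No age limit, activation or shock condition is given.
- **RBC and FFP (prospective).** "All trauma patients who have started or have received at least one RBC and FFP unit in the pre-hospital setting because of haemorrhage". This cohort comes from Newcastle and Oxford. Again there is no age limit, activation or shock condition.

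Section 7.2 lists no exclusions, so nothing there evens out the rules.

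Other places describe the RBC cohort differently. The synopsis has "Patients who have received at least one RBC unit in the pre-hospital setting because of trauma haemorrhage between March 2015 and April 2018". Section 8 says the RC&Plasma data will be "compared with historical data of RBC transfusion in the pre-hospital setting in London from March 2015 to April 2018". The retrospective part of section 9.2 refers to "trauma patients who have received RBC transfusion in the pre-hospital setting in London". None of the three mentions the ED. The synopsis also puts the activation and shock conditions on the air-ambulance RBC and FFP patients, whereas section 7.1 does not.

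The ED appears once more on the prospective side: the Part 1 heading of Table 1 in section 9.2 covers transfusion in the pre-hospital "setting (or emergency department for RLH").

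**The concern.** The secondary objective compares RC&Plasma with RBC alone, and with RBC plus FFP, on base deficit, coagulation, transfusion requirement, length of stay and survival. Such a comparison can be interpreted only if the groups would have been comparable under the same treatment. Entry rules that differ by cohort undermine that before any treatment effect arises.

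The outcome used for the power statement in section 10.1 is the proportion arriving in the ED with a base deficit above 6 mEq/L. It is measured on arrival. A patient whose first unit is given in the ED therefore contributes a value that predates the product. Read literally, section 7.1 admits such a patient to the RBC cohort but not to the RC&Plasma cohort, which needs a pre-hospital unit.

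Two people extracting retrospective data, one from section 7.1 and one from the synopsis, could also assemble different cohorts.

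**Working it through.** **1. The plan's own figure.** Section 10.1 assumes 160 RBC and at least 60 RC&Plasma patients, a rate of 70% against 50%, and 80% power. Section 10.2 makes tests two-sided at 5%.

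- Pooled rate = (160 × 0.70 + 60 × 0.50)/220 = 142/220 = 0.645.
- SE under no difference = √[0.645 × 0.355 × (1/160 + 1/60)] = 0.0724.
- SE under the alternative = √[0.70 × 0.30/160 + 0.50 × 0.50/60] = 0.0740.
- Power = Φ[(0.20 − 1.96 × 0.0724)/0.0740] = Φ(0.784) = 78.4%.

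The unpooled version gives 77.1% and Fisher's exact test 75.9%. The stated 80% is approximately reproduced and is not in dispute.

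**2. Entry rules side by side.**

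| Condition | RC&Plasma (7.1) | RBC (7.1) | RBC (synopsis, 8, 9.2) | RBC+FFP (7.1) | RBC+FFP (synopsis) |
|---|---|---|---|---|---|
| Age over 1 year | yes | no | no | no | no |
| Activation | yes | no | no | no | yes |
| Haemorrhagic shock | yes | no | no | no | yes |
| Place of transfusion | pre-hospital | pre-hospital, with RLH ED added | pre-hospital | pre-hospital | air ambulance |
| Components needed | one | one | one | both | both |

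Three differences emerge. The first three conditions bind only RC&Plasma in section 7.1. The ED addition for RBC conflicts with three other statements of the same cohort. RBC+FFP entry depends on both components having been begun, while one bag is enough for RC&Plasma.

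**3. Could the size of an ED effect be computed?** It would need the share *f* of ED-only patients in the RBC cohort and their rate *q* of base deficit above 6. The protocol gives neither. The mixed RBC rate is 0.70(1 − *f*) + *qf*. The ranges below are assumptions for illustration only: *f* from 10% to 50%, *q* from 40% to 80%, and 70% taken as the pre-hospital rate.

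- *f* = 0.5, *q* = 0.4: 0.35 + 0.20 = 55%. With no treatment effect, RC&Plasma at 70% would look 15 points worse. Power for a true 70% to 50% effect at 160/60 would be about 10%.
- *f* = 0.1, *q* = 0.5: 0.63 + 0.05 = 68%. RC&Plasma would look 2 points worse, with power 69%.
- *f* = 0.5, *q* = 0.8: 0.35 + 0.40 = 75%. RC&Plasma would look 5 points better, with power about 94%.

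The sign depends on whether *q* lies below or above 70%, which the protocol does not reveal.

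**4. Are ED-only cases needed for numbers?** Section 10.1 gives 70 pre-hospital RBC patients a year. March 2015 to April 2018 inclusive is 38 months.

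- Expected: 70 × 38/12 = 222.
- After the 25% loss in section 10.1: 222 × 0.75 = 166, which still covers the 160 assumed.

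**The case against.** The strongest reply is that the ED phrase is loose wording and not a working rule. Three other places say pre-hospital, and section 9.1 has laboratories notify the central team of pre-hospital transfusions, so ED-only cases have no obvious route in. The phrase could even mean patients transfused in both places. The ED ambiguity also touches RC&Plasma: section 7.1 allows activation by the RLH trauma team lead, section 8 makes the component available in the hospital, and Table 1 covers ED transfusion there. All of this stands, and it makes the ED element a contradiction to be reconciled and not a settled inclusion. It does not make the rules equal, because the last RC&Plasma bullet still requires a pre-hospital unit and the RBC rule has no matching limit.

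Section 10.2 plans multivariable adjustment with an open list of confounders. That helps with case mix, but the model is named only for RC&Plasma against RBC. Nor can covariates make an arrival measurement respond to a product given later.

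A reader might infer that the RBC comparison is diluted by a known amount, or that requiring both components gives RBC+FFP a survival advantage of known size. The documents support neither. The inputs for the first are absent. For the second, having both components begun defines the strategy under comparison, and the wording asks only that they be started. The protocol gives no share of patients who die or reach hospital before the second component. Its only candidate mortality figure, 27%, is London pre-hospital mortality in 2015 (section 5.1.1), not 24-hour or 28-day mortality. The selection is possible, and section 5.1.1 itself notes that giving both components at the scene adds complexity and may delay transfer, but its size is unknown.

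**Conclusion.** The point holds as a defect of eligibility wording that leaves the secondary clinical comparisons open to selection bias. Two parts are certain from the text: section 7.1 applies age, activation and shock to one cohort only, and its ED addition contradicts the synopsis, section 8 and section 9.2. The bias in the ED-arrival base-deficit comparison is conditional on ED-only recipients actually entering the RBC cohort. Its direction and size cannot be determined from the protocol; the 15-point and 5-point extremes above come from assumed inputs and show only that either sign is possible.

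It would be too strong to say that the study's conclusions are biased. The primary endpoints are on-time-in-full delivery and wastage, and no progression criterion in section 10.3 uses a between-cohort clinical comparison. The matter still deserves correction, because these comparisons are a stated objective of work meant to prepare a future trial, and the correction is cheap. The finding that ED-only cases are not needed rests on the protocol's average of 70 a year holding across the retrospective window.

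**What to change.** - Reconcile the synopsis, section 7.1, section 8, and section 9.2 (Table 1 and the retrospective part), so that each cohort has one definition.
- Limit all between-cohort clinical comparisons to patients over 1 year old whose first unit was started or received pre-hospital for traumatic haemorrhage. Remove the ED parenthesis from the RBC comparator. Keep ED-only recipients for the usage and wastage metrics.
- Apply activation and shock to all cohorts where the records allow. Where they do not, apply them to none in the comparison.
- Where laboratory records permit, report a sensitivity analysis that adds Newcastle and Oxford patients in whom only one component was begun pre-hospital. Admitting them to the main comparison would change the question from treatment received to strategy intended, so a sensitivity analysis is the better place.

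The cost is slightly fewer retrospective RBC cases (about 166 expected after loss, against 160 assumed) and some case-note work. A filter on laboratory records alone will not do: activation and shock are neither among the items that laboratories report under section 9.1 nor listed in Table 1, so they would have to be abstracted from the notes.

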7.2. Exclusion criteria

None

8. Study design

Feasibility, observational cohort study.

RC&Plasma transfusion will replace RBC transfusion in the pre-hospital setting in London, and will be available for transfusion in hospital at RLH for trauma patients >1yrs old. Operational and clinical data relating to administration of RC&Plasma component will be compared with historical data of RBC transfusion in the pre-hospital setting in London from March 2015 to April 2018.

Newcastle and Oxford hospitals will continue to administer RBC and FFP transfusion in the pre-hospital setting.

9. Study procedures

9.1. Case Identification

In the UK, it is a legal requirement that all hospital blood transfusion laboratories have a system in place to document the final destination of every blood component issued, so that any probable recipient-related transfusion complications (e.g. infections) can be traced back to donors, so that appropriate measures can be taken (BSQR 2005). These records must be kept in the transfusion laboratories for 30 years.

Therefore, all cases will be identified from the transfusion laboratories at three sites - the RoyaL London Hospital (RLH), John Radcliffe Hospital, Oxford and Royal Victoria Infirmary,

Newcastle Hospital. The RLH supplies blood to pre-hospital team for whole of London, and therefore RLH laboratory will keep records of all units issued and transfused (see diagram below).

Transfusion laboratories will only inform the central team at Barts Health of the date/time when blood was transfused in the pre-hospital setting, the name of hospital that the patient was admitted to, and the unique donation number of the transfused units. No patient' identifiers will be given to the central team. Once the central team has been informed of the case, the clinical team on the relevant site will be contacted and asked to submit the case report form (CRF) for the identified case using patient's case notes.

Study Scheme Diagram

Transfusion form handed over from Trauma Team to transfusion laboratory

Cases identified from the transfusion laboratory

Case report form completed by clinical team at:

a) 24 hours and b) 30 days, or discharge or death – whichever occurs first

9.2. Data collection

Operational data

Operational data regarding the deliverability and supply of blood will be collected on monthly basis from NHSBT and transfusion laboratory.

Clinical data (prospective)

Data will be collected from the clinical team at six sites. Once a case has been identified, the clinical team on each site will be asked to complete the CRF for case using a unique identification number – this will be a sequential number for each site. The completed CRF will be emailed to the central team at Barts Health Trust using nhs.net email accounts.

Study cases will not be contacted or approached for consent and NO identifiers (i.e. names, addresses, dates of birth, hospital or NHS numbers, or date of death) will be sought in the CRF. Respondents will be asked to keep their own record of the unique study number and the patient identifiers in order to facilitate elimination of duplicate reports or raise further gueries if required.

The CRF will be made up of two parts and will seek information as described in Table 1.

Table 1.	Variables that will be collected on the Case Report Form	
Part 1: At	presentation and within 24 hrs of blood transfusion in pre-hospital	
setting (or emergency department for RLH)		
- Gen	der and age	

- Co-morbidities

- Date of transfusion for RC&Plasma (and RBC and FFP)
- Number of units transfused (or ml/Kg for children)
- Donation number for each RC&Plasma transfused
- Amount of crystalloid/colloid administered in 24 hours
- Severity of injury
- Laboratory results (Haemoglobin, platelet, coagulation tests, lactate results) from scene to ED and within 24 hours
- Patient's blood group
- Blood transfusion requirements in the first 24 hours
- Time of death (in hours) from administration of RC&Plasma (or RBC only, or RBC and FFP), and cause of death
- Transfusion reactions

Part 2: At 30 days, or discharge, or death or transfer to another hospital, (whichever is first)

- Date of discharge
- Thrombotic event (arterial or venous)
- Blood transfusion requirements
- Transfusion reactions
- Number of ventilator free days
- Number of intensive care units-free days
- Hospital length of stay
- Time of death (in days) from administration of RC&Plasma (or RBC and FFP), and cause of death

Retrospective data

Similar information as described in Table 1 will also be collected for trauma patients who have received RBC transfusion in the pre-hospital setting in London between March 2015 to April 2018. Cases will be initially identified from transfusion laboratories at RLH, and once the case has been identified other sites will be asked to submit anonymised clinical information on identified cases using patient's clinical notes and patient's electronic data.

Each case will be given a unique identifier, and no patient's identifier will be collected on the CRF or transferred to the central team at Barts Health.

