- a. assess if it's feasible to deliver RC&Plasma component to patients who are bleeding in the pre-hospital setting, so that we can lay the groundwork for a future trial that will compare the efficacy and safety of different transfusion strategies
- b. evaluate the impact of the RC&Plasma transfusion in trauma bleeding patients in the pre-hospital setting on: transfusion requirements, rate of haemolysis, resuscitative effect, days in hospital, rate of thrombosis, and mortality by comparing these with RBC transfusion only (using retrospective data) and RBC and FFP transfusion (prospective data from Newcastle and Oxford hospitals);

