6.2. Secondary objective

Compare the impact of RC&Plasma transfusion with RBC transfusion (retrospective data between March 2015 to April 2018) and RBC and FFP transfusion (prospective data from Newcastle and Oxford hospital) on: resuscitative effect (base excess, lactate), coagulation parameters, overall transfusion requirement, haemolysis, days in hospital and mortality, in trauma bleeding patients.

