6.4. Secondary endpoint

To evaluate the clinical impact of RC&Plasma transfusion versus RBC transfusion and RBC and FFP transfusion, the following clinical data will be collected:

- Changes in base deficit and prothrombin time from scene to emergency department
- Transfusion wastage (red blood cells, fresh frozen plasma, platelets, cryoprecipitate) at 24-hours post injury
- Transfusion requirement at 24 hours and up to hospital discharge or 28 days, or death whichever occur first
- Total hospital length of stay
- Survival analysis up to 24-hours and 28 days post injury

Other factors that will be monitored include: *NHSBT*

- Wastage (units per month)
- Substitutions (units per month)
- Impact on supply of other blood components
- Impact on other processes
- Additional administration resources and time required to provide RC&Plasma

Hospital

- Additional administration support and time required to support clinical team
- % of RC&Plasma used in the pre-hospital setting
- % of RC&Plasma used in emergency department

7. Study population

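### Haemolysis is promised as a three-cohort comparison, but it is not a section 6.4 endpoint and Table 1 gives it no field or marker (minor)

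*Protocol*

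**What the plan says.** Three places in the protocol make haemolysis a comparative outcome:

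- The synopsis (section 4) lists, for comparison between the cohorts, "overall transfusion requirement, haemolysis, days in hospital and mortality, in trauma bleeding patients".
- Overall objective b in the Introduction (section 5) words it as a rate: "transfusion requirements, rate of haemolysis, resuscitative effect, days in hospital".
- Section 6.2 repeats it among "coagulation parameters, overall transfusion requirement, haemolysis, days in hospital and mortality, in trauma bleeding patients".

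Section 6.4, which sets out the clinical data for the comparison, opens with "Changes in base deficit and prothrombin time from scene to emergency department". It continues with component wastage, transfusion requirement, length of stay and survival. Haemolysis does not appear.

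Section 9.2 fixes the content of the form: "The CRF will be made up of two parts and will seek information as described in Table 1". The laboratory line of that table reads "Laboratory results (Haemoglobin, platelet, coagulation tests, lactate results) from scene to ED and within 24 hours". The entry closest to haemolysis, present in both Part 1 and Part 2, is "Transfusion reactions". For the historical RBC cohort, section 9.2 states: "Similar information as described in Table 1 will also be collected for trauma patients". The same content therefore carries over to the retrospective arm.

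**The concern.** An outcome stated three times as something to be compared should be traceable to an endpoint and to a data item. Haemolysis reaches neither. An analysis plan can define how haemolysis is classified and summarised, but it cannot analyse information that the form never sought. This is therefore a gap in the protocol and not a detail properly left for later.

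At stake is one secondary safety comparison. It has some weight because section 5.1.1 says the component's safety has not been compared with that of standard components, and the study is meant to prepare a trial of efficacy and safety. A table of unclassified transfusion reactions would not answer the question that objective b asks.

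**Working it through.** No figure in the protocol is disputed on haemolysis, so the check sets the lists side by side.

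**Step 1. Trace each outcome in section 6.2.**

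| Outcome in 6.2 | In 6.4? | In Table 1? |
|---|---|---|
| Base excess | yes (base deficit) | no |
| Lactate | no | yes |
| Coagulation parameters | yes (prothrombin time) | yes |
| Transfusion requirement | yes | yes |
| Haemolysis | no | no |
| Days in hospital | yes | yes |
| Mortality | yes (survival) | yes (time of death) |

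Section 6.4 covers 5 of 7 and Table 1 covers 5 of 7. Six of the seven appear in at least one list. Haemolysis is the only one in neither.

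**Step 2. Compare with thrombosis.** Objective b promises a rate of haemolysis and a rate of thrombosis in the same sentence. Thrombosis is also absent from section 6.4, but Part 2 of Table 1 gives it its own entry, split into arterial and venous. Haemolysis has no counterpart.

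**Step 3. Look for indirect capture in Table 1.**

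- Transfusion reactions: as listed, no type is asked for. A recognised haemolytic reaction may be included, but could not be told apart from other reactions.
- Haemoglobin: falls with bleeding and rises with transfusion, so it is not specific to haemolysis in these patients.
- Patient's blood group and the donation number of each RC&Plasma unit: useful for investigating a suspected reaction, but not outcomes.

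**Step 4. Look outside the form.** Sections 11.1 and 14 send transfusion-related adverse events to the national schemes as routine care. The protocol describes no route from those reports back into the study database. These sections do not stop the form from recording reactions, but they do not supply the missing item either.

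**Step 5. Base deficit and the stated power.** The Table 1 laboratory line omits base deficit, on which section 10.1 sizes the clinical comparison, so I checked whether the sizing is affected. Inputs from sections 10.1 and 10.2: 70% against 50%, two-sided 5%, 160 RBC and 60 RC&Plasma patients.

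Power = Φ[(0.20 − 1.96·s0)/s1], where s0 = √[p̄(1−p̄)(1/n1+1/n2)] and s1 = √(0.70·0.30/n1 + 0.50·0.50/n2).

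- Plan's own figure, n1 = 160 and n2 = 60: p̄ = (112+30)/220 = 0.645, s0 = 0.0724, s1 = 0.0740. Power = Φ(0.784) = 78.4%, against the stated 80%. It reproduces closely.
- After the stated 25% loss from the planned 200 and 140: n1 = 150 and n2 = 105. Here p̄ = 0.618, s0 = 0.0618, s1 = 0.0615. Power = Φ(1.28) = 90%.
- With 105 RC&Plasma patients, 84 RBC patients with a value (84/200 = 42%) still give 80%.

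The sizing has ample room and is not part of the criticism.

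**The case against.** The strongest reply is that objective b never says haemolysis is defined by laboratory tests. Transfusion reactions are recorded in both parts of the form for every case, so recognised haemolytic reactions divided by patients transfused would be a legitimate rate. A one-line list need not show every sub-item of a form, and the form itself is not shown. Sites also keep the key linking study number to patient so that queries can be raised, and the data come from notes and electronic records, so nothing unrepeatable is lost.

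Much of this stands. A rate of recognised haemolytic reactions would be reportable if the reaction type were recorded, and later queries are possible. So a reader might infer that the study can never report haemolysis, but the protocol does not support that. What remains is that Table 1, as written, does not ask for type, and a later query still needs a decision on what to ask.

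A second reply is that absence from section 6.4 proves little, because lactate and thrombosis are absent there too. That is fair, and it is why the point rests on absence from both lists.

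A reader might also infer that base deficit will not be collected and that the sample size calculation therefore fails. The protocol does not support this. Section 6.4 says changes in base deficit are among the clinical data to be collected, and section 10.1 allows for missing samples. The omission from the laboratory line is an inconsistency between lists. Nor can one say that completeness in the RBC cohort is tight: setting 150 remaining RBC patients against the 160 assumed ignores that the 160 is paired with only 60 RC&Plasma patients, whereas 105 would remain.

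**Conclusion.** The point holds in a limited form. Haemolysis is a comparative objective in three places, is missing from section 6.4, and has no field or marker in Table 1. It is the only one of the seven section 6.2 outcomes named in neither list. Followed as written, the form would yield unclassified transfusion reactions and would not support the promised comparison across the three cohorts, although the information could partly be recovered by querying sites.

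This assumes that the form follows Table 1, as section 9.2 says it will. If the actual form already records reaction type or haemolysis tests, only the protocol wording needs correcting.

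Severity is minor: one secondary comparison in an observational feasibility study. The primary endpoints (delivery and wastage), the progression criteria and the stated power are unaffected. The base deficit omission is a consistency note only.

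**What to change.** **Haemolysis.** Add it to section 6.4 and to Table 1 for all three cohorts, from existing records only and with no new blood samples:

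- type of transfusion reaction, with haemolytic yes/no;
- whether a routine haemolysis test was done;
- its result and its time after transfusion.

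Report the number tested and the number with haemolysis in each cohort, with 95% confidence intervals, and label the comparison descriptive. If routine tests prove too sparse, withdraw haemolysis from the synopsis, objective b and section 6.2 instead.

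**Base deficit.** Add it to the Table 1 laboratory line, at scene where available and on emergency department arrival, to match sections 6.4 and 10.1.

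**Cost.** A wording amendment and a few extra abstraction fields, best settled before abstraction starts. The main drawback is that test data may be sparse and tested patients a selected group, above all in the retrospective RBC cohort, so any difference between cohorts would need cautious reading.
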